3.4 Secondary endpoints/outcomes

The Beta (β) angle and Delta (δ) angle in degrees

4. STUDY DESIGN

Controlled trial without randomisation

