1.4 Treatment / Intervention (if applicable)

Magnetic resonance imaging (MRI) can safely be used to assess the upper airway anatomy and would allow measurement of the axes described to suggest which head and neck position would provide best anatomical alignment to reduce anterior impingement.

All the MRI scans will be conducted using 3.0 Tesla (Optima 750w, GE Medical, Milwaukee, WI, USA) using the cervical spine section of the coil. T2-weighted images in the sagittal plane will be acquired using a fast recovery fast spin echo (FRFSE) technique with the parameters in Table 1. The scans will take around two and half minutes and a member of the anaesthetic investigator team will be present to facilitate positional changes and maintain consistency.

Acquisition parameters (Table 1):

Repetition time (TR)	2905 ms
Echo time (TE)	107ms
Field of view (FOV)	36 cm
Slice thickness	3 mm
Slice gap	1 mm
ETL	19
Frequency matrix size	352
Phase matrix size	320
Number of excitations (NEX)	3
Receiver band width	41.67 kHz
Scan time	2 min 34 s

MRI scanning will be performed in following 3 head and neck positions:

Neutral position- Participant lying flat on the MRI table, with a vertical gaze, without any pillow (no flexion, no extension of the neck).

Sniffing position is achieved with head resting on Oxford HELP headrest (Alma Medical, London) of 7cm in height to achieve neck flexion by 35° and extension at atlantooccipital joint to achieve face plane extension of 15° (Horton WA 1989)

Extension position: Oxford HELP Base pillow (Alma Medical, London) is placed under the shoulders with head resting off the end and neck in full extension position.

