7. TRIAL PROCEDURES

Screening

Step 1 – Convenience sampling used to recruit participants (UHCW Staff) by the investigators. Inclusion and exclusion criteria will be discussed. Aim to recruit 2 participants every week. We anticipate this phase will take 10 -12 weeks.

Baseline

Step 2- Information leaflet provided and study outcomes discussed. MRI safety questionnaire also reviewed by the potential participant. Any reasons that would preclude positioning in an MRI machine will also be recorded.

Participants will be allowed to enough time to read and understand the participant information. The procedure for any abnormal findings will be discussed in consent and in the participant information sheet.

Step 3 – For participants who would like to volunteer, consent form signed. Any queries clarified. Baseline demographic and airway assessment recorded. This data will be stored securely within the research locker located in the Anaesthetic department, UHCW.

Pre-booked MRI slot in the future is allocated to the participant.

Step 4 - Participants will be reminded about MRI slot 1 day prior to scan

MRI Suite

Step 4 – Participants attend MRI Suite, UHCW Radiology department at specified time. MRI Safety questionnaire reviewed again and completed for Radiology department. Any remaining questions answered by anaesthetic investigators and/or radiographer.

Step 5 – MRI Conduct. Anticipate each scan will take 2.5 minutes (total 7.5 minutes for 3 scans), with re-positioning in the middle by one of the Anaesthetic investigators. Including questions and filling out questionnaire anticipate this will take 30 minutes per participant in total.

There is capacity to scan 2 participants per week on 1 per pre-booked MRI slot and therefore this phase will take at the minimum 10 to 12 weeks.

Participant involvement ends with MRI scan in the final head and neck position.

Review

Step 6 – This sequence will produce three sagittal MRI images per participant. These images will have their personal data removed and will be pseudo-anonymised (tokenization) after the images have been reviewed for any abnormal findings and the angles will be measured by the Consultant Radiologist.

Step 7 – Tokenized results analysed by Anaesthetic investigator team

Step 8 – Further anonymised data will be analysed by the statistician and anticipate this will take another 6 -8 weeks.

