7.1.1 Screening

Participants will be provided information regarding preparation for an MRI and questions related to this will be answered by the lead radiographer.

Standard operating procedure for patients undertaking an MRI will be followed and led by the radiographer present. At the scan, a member of the anaesthetic investigator team will be present to re-confirm (verbal) consent and facilitate the scan by ensure consistency between positions.

The patient will undergo three MRI scans. At the end of this the participant will be thanked for their involvement. We will state that if they have any questions to contact the research team and if they would like results of the study they can be contacted in the future.

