8.3 Statistical analysis plan

8.3.1 Primary outcome analysis

Data will be analysed using ANOVA or appropriate test and p value less than 0.05 was considered statistically significant

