9.2 Data handling and record keeping

All participant data will be handled by the investigator team (MRI radiographer, Consultant Radiologist and Anaesthetic investigator team), and protected on UHCW trust server which is username and password protected.

In terms of the MRI images, these will not be linked to the volunteer's real hospital data. We aim to keep confidentiality by coding each participant (pseudo anonymisation), and each scan (i.e. participant 1, first scan = 1A, second scan = 1B etc).

Hard copies of informed consent will be stored in a locked cabinet within the Anaesthetic department at UHCW. MRI safety questionnaires will be stored as per standard Radiology policy for Information Governance. Personal data will be collected for consent and safety checklists. Access to this data will be by the research team and radiographer to ensure safety check list is correctly completed.

All local investigators will be trained in accordance with the UK Policy Framework for Health and Social Care Research.

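### Scan order is neither specified, randomised nor modelled, so position could be completely confounded with the order of the three scans

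*Combined protocol and SAP*

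**What the plan says.** The design section (Section 4) consists of one phrase: "Controlled trial without randomisation". Section 1.4 states that "MRI scanning will be performed in following 3 head and neck positions" and then describes neutral, sniffing and extension, without saying that this list is the scanning sequence. Section 7.1.1 confirms that every participant has all three: "The patient will undergo three MRI scans". Step 5 of Section 7 puts them in a single session: "Anticipate each scan will take 2.5 minutes (total 7.5 minutes for 3 scans), with re-positioning in the middle by one of the Anaesthetic investigators". The same section closes the visit without naming the last position: "Participant involvement ends with MRI scan in the final head and neck position".

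Section 9.2 codes images by sequence ("participant 1, first scan = 1A, second scan = 1B etc") but does not tie a letter to a position. For the primary outcome, Section 8.3.1 says "Data will be analysed using ANOVA or appropriate test and p value less than 0.05". Section 8.3.2 is equally general for the secondary angles. Neither mentions scan order or period.

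**The concern.** The primary comparison is the within-participant difference in alpha angle between positions, and Section 2.2 intends to recommend a head and neck position from it. Comparing each participant with themselves removes differences between people. It does not remove differences between the first, second and third scan. Settling on the table, muscle relaxation or residual posture from the preceding position could each produce such a difference.

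The plan leaves two possibilities open.

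- **One common order for everyone.** Any order effect is then added to the position effect and cannot be removed by analysis.
- **An order chosen by the operator.** The choice may be selective. Adjustment then works only if the orders vary enough and are recorded and modelled.

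At stake is whether an observed difference in angle can be attributed to position.

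**Working it through.** **Inputs from the documents.** 20 participants (Section 8.1), 3 positions each in one session (Sections 1.4, 7, 7.1.1), significance level 0.05 (Section 8.3.1). The documents give no SD, expected difference or drift, so drift is an assumption and is shown over a range. There is no figure in the plan on this point to reproduce.

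**1. Can position be separated from order?** Take the model participant + position + scan period, with period as an unrestricted factor. There are 20 × 3 = 60 observations and 20 + 2 + 2 = 24 columns. Variance is for a difference between two positions, relative to the model without period, where it is 2/20 = 0.10 in units of the residual variance.

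| Allocation of 20 participants | Rank (of 24) | Relative variance |
|---|---|---|
| One common order | 22 | position not separable from period |
| 10 in one order, 10 in its reverse | 23 | middle position still aliased |
| 18/1/1 over three cyclic orders | 24 | 3.60 |
| Six orders, 3 or 4 each | 24 | 1.000 to 1.008 |

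With one common order the two period columns duplicate the two position columns, hence 24 − 2 = 22. With six orders the error degrees of freedom are 60 − 24 = 36, against 60 − 22 = 38 without a period term.

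**2. What would an order effect do under one common order?** Assume no true position effect and a linear drift of *d* per scan, in units of the SD of the paired difference, with equal correlation between scans. The paired difference has variance 1, so the residual variance is 0.5.

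- Repeated-measures ANOVA: noncentral F on 2 and 38 df, with λ = 20 × (1² + 0² + 1²) × d² / 0.5 = 80d². For example, d = 0.10 gives λ = 0.8 and d = 0.25 gives λ = 5.0.
- Paired t-test, 19 df, two-sided: noncentrality = bias × √20. The bias is 2d for first v third scan and d for adjacent scans. For d = 0.10, first v third, this is 0.20 × 4.472 = 0.894.

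False-positive rates:

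| d (assumed) | ANOVA | First v third scan | Adjacent scans |
|---|---|---|---|
| 0.02 | 5% | 5% | 5% |
| 0.05 | 6% | 7% | 6% |
| 0.10 | 11% | 14% | 7% |
| 0.20 | 32% | 40% | 14% |
| 0.25 | 47% | 56% | 19% |

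A simulation of 40,000 trials at d = 0.02, 0.10, 0.20 and 0.25 gave ANOVA rates of 0.052, 0.110, 0.319 and 0.469, in agreement.

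**3. What does varying the order achieve by itself?** With three participants in each of six orders, 18 participants are exactly balanced. If the other two take different orders, the mean scan number of any two positions differs by at most (2 + 1)/20 = 0.15. So even without a period term at most 0.15d remains in any pairwise contrast, against 2d for first v third in a fixed order.

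**The case against.** The harm is hypothetical. The endpoint is a geometric angle on a static image, not a response that is learned, fatigues or wears off. Section 1.4 defines each position physically and has an investigator present to keep positioning consistent, so posture is actively re-set before each scan, and total scanning time is only 7.5 minutes. The three postures are deliberately very different, so a true position effect may dwarf any drift. The drift figures are in units of an unknown SD, cannot be converted to degrees, and run from no consequence to a serious one with nothing in the documents to favour either end. The design label in Section 4 does not prove that a fixed order will be used, the general wording in Section 8.3.1 does not rule out an order term, and the scan codes already record sequence. Finally, if drift is linear, reversing the order for half the participants is enough: with a linear period term that design has full rank (23 of 23 columns) and no loss of precision.

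Most of this stands as a limit on weight. An order effect may well be small, and the tabulated rates do not measure this trial's risk. It does not close the gap. Consistent set-up controls variation in positioning, not order. The documents give no expected difference or SD from which to argue that drift would be negligible, and pairs of positions with similar angles are the most exposed. Sequence codes do not help without a link to position, and an order term is of no use if the order never varies. The half-and-half reversal relies on drift being linear; six orders do not, at almost no extra cost.

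**Conclusion.** The concern holds. No section fixes, randomises, counterbalances or models the scan order, and the plan permits a single common order under which position and order cannot be separated (rank 22 of 24). That result is structural and needs no assumption beyond the common order itself, which the documents allow but do not state.

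The size of any bias is unknown. Under the assumed linear drift with no true position effect, it ranges from negligible at 0.02 SD per scan to a 47% ANOVA false-positive rate at 0.25 SD. This is an unguarded risk, not a demonstrated bias. The change is worth making because it is inexpensive and because a common order cannot be corrected after the data are collected.

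**What to change.** - Generate a random list in advance that allocates each participant to one of the six position orders, 3 or 4 participants per order. Exact balance would need a multiple of six, such as 18 or 24; near balance with 20 is adequate.
- Record on the CRF the order used and the position belonging to each scan code.
- Specify the primary model as participant, position and scan period, and use the same model for the secondary angles.
- Describe the design in Section 4 as a within-participant (crossover) study with randomised scan order.

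The period term removes drift common to the session. Carry-over from the preceding position is nearly balanced across positions with 20 participants; it is not removed.

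**Cost:** a one-page list, one CRF field and some rewording, with the same three scans, scanner time and sample size. The headrest set-up sequence will vary between participants. Two of 38 error degrees of freedom go to period, and the variance of a position difference rises by at most 0.8%.

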5. STUDY SETTING

Single centre study at University Hospitals Coventry and Warwickshire NHS Trust

6. ELIGIBILITY CRITERIA

6.1 Inclusion criteria

- Able to provide consent
- Volunteers, UHCW staff, aged > 18 years
- Medically able and willing undertake MRI scanning.

- Should pass the MRI safety check list to enter the MRI suite. All participants will complete an MR safety questionnaire immediately prior to their MR scan

6.1 Exclusion criteria

- Unable to provide consent
- Not willing to have MRI scan or unable to undergo MRI scanning and restricted neck movements. For MRI safety reasons all participants with a cardiac pacemaker or other electronic implants will be excluded from the study.

7. TRIAL PROCEDURES

Screening

Step 1 – Convenience sampling used to recruit participants (UHCW Staff) by the investigators. Inclusion and exclusion criteria will be discussed. Aim to recruit 2 participants every week. We anticipate this phase will take 10 -12 weeks.

Baseline

Step 2- Information leaflet provided and study outcomes discussed. MRI safety questionnaire also reviewed by the potential participant. Any reasons that would preclude positioning in an MRI machine will also be recorded.

Participants will be allowed to enough time to read and understand the participant information. The procedure for any abnormal findings will be discussed in consent and in the participant information sheet.

Step 3 – For participants who would like to volunteer, consent form signed. Any queries clarified. Baseline demographic and airway assessment recorded. This data will be stored securely within the research locker located in the Anaesthetic department, UHCW.

Pre-booked MRI slot in the future is allocated to the participant.

Step 4 - Participants will be reminded about MRI slot 1 day prior to scan

MRI Suite

Step 4 – Participants attend MRI Suite, UHCW Radiology department at specified time. MRI Safety questionnaire reviewed again and completed for Radiology department. Any remaining questions answered by anaesthetic investigators and/or radiographer.

Step 5 – MRI Conduct. Anticipate each scan will take 2.5 minutes (total 7.5 minutes for 3 scans), with re-positioning in the middle by one of the Anaesthetic investigators. Including questions and filling out questionnaire anticipate this will take 30 minutes per participant in total.

There is capacity to scan 2 participants per week on 1 per pre-booked MRI slot and therefore this phase will take at the minimum 10 to 12 weeks.

Participant involvement ends with MRI scan in the final head and neck position.

Review

Step 6 – This sequence will produce three sagittal MRI images per participant. These images will have their personal data removed and will be pseudo-anonymised (tokenization) after the images have been reviewed for any abnormal findings and the angles will be measured by the Consultant Radiologist.

Step 7 – Tokenized results analysed by Anaesthetic investigator team

Step 8 – Further anonymised data will be analysed by the statistician and anticipate this will take another 6 -8 weeks.

7.1 Recruitment

Staff members of University Hospitals Coventry and Warwickshire NHS Trust (UHCW) will be invited to participate as volunteers in this study. This will be sampled conveniently, and the inclusion and exclusion criteria will be checked. They will then review the MRI safety check list for eligibility to undergo MRU scan. Written informed consent will be obtained from the participants.

7.1.1 Screening

Participants will be provided information regarding preparation for an MRI and questions related to this will be answered by the lead radiographer.

Standard operating procedure for patients undertaking an MRI will be followed and led by the radiographer present. At the scan, a member of the anaesthetic investigator team will be present to re-confirm (verbal) consent and facilitate the scan by ensure consistency between positions.

The patient will undergo three MRI scans. At the end of this the participant will be thanked for their involvement. We will state that if they have any questions to contact the research team and if they would like results of the study they can be contacted in the future.

7.1.2 Payment

No payment will be offered for volunteers to this study

7.2 Consent

A written consent will be obtained from all participants. All investigators will be suitably trained to obtain consent as per Good Clinical Practice.

MRI safety questionnaire as per Radiology Information Governance also required.

7.3 Baseline data

Baseline demographic data:

- Age
- Sex

- Ethnicity
- Height
- Weight

Baseline airway assessment data:

- Mallampati score
- Jaw protrusion
- Neck movement
- Thyromental distance
- Sternomental distance

7.4 Long term follow-up assessments

No long-term follow-up is planned for this study.

7.5 End of study definition

This will occur when the 20th patient has their final MRI study performed

8. STATISTICS AND DATA ANALYSIS

8.1 Sample size calculation

Previous studies on volunteers involving radiological imaging recruited 8 , 15 and 42 patients (Adnet. et al, Abramson. et al and Greenland. et al). We aim to recruit 20 volunteers (UHCW staff) to participate in the study.

8.2 Planned recruitment rate

We plan to recruit 10 volunteers every 4 weeks, totally 8 weeks. This will total 20 participants. Recruitment will be undertaken by each of the three Anaesthetic investigators and therefore this is a realistic target due to the relatively small number of participants required.

8.3 Statistical analysis plan

8.3.1 Primary outcome analysis

Data will be analysed using ANOVA or appropriate test and p value less than 0.05 was considered statistically significant

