3. OBJECTIVES AND OUTCOME MEASURES/ENDPOINTS

3.1 Primary objective

- Measurement alpha (α) angle between the tracheal axis (TA) and laryngeal axes (LA) in three different positions.

The primary objective is to identify which of the three head and neck positions we have identified ("sniffing", extension of neck and neutral position) improves the alpha angle when examined under MRI. We hypothesise the position that most improves the alpha angle would reduce the incidence of anterior impingement with videolaryngoscopy. We hypothesise the position that brings the alpha angle closest to 180° would reduce the incidence of anterior impingement and therefore considered best for tracheal intubation using VL.

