8.3.2 Secondary outcome analysis

Data will be analysed using ANOVA or appropriate test and p value of 0.05 or less will be considered statistically significant

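### Every participant is measured in all three positions, but the plan does not specify a within-participant analysis: sections 8.3.1 and 8.3.2 leave open an ANOVA that ignores the matching

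*Combined protocol and SAP*

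**What the plan says.** The design is within-participant throughout. Section 1.4 lists the three head and neck positions. Section 7.1.1 states "The patient will undergo three MRI scans", and Step 6 of section 7 states "This sequence will produce three sagittal MRI images per participant". The primary objective in section 3.1 is "Measurement alpha (α) angle between the tracheal axis (TA) and laryngeal axes (LA) in three different positions". The sample size in section 8.1 is "We aim to recruit 20 volunteers (UHCW staff) to participate in the study", justified by the sizes of earlier imaging studies.

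The primary analysis, section 8.3.1, reads in full: "Data will be analysed using ANOVA or appropriate test and p value less than 0.05 was considered statistically significant". Section 8.3.2, for the beta and delta angles, reads: "Data will be analysed using ANOVA or appropriate test and p value of 0.05 or less will be considered statistically significant".

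Section 4 describes the design only as "Controlled trial without randomisation". Nowhere do the documents mention repeated measures, pairing, a participant effect, a mixed model or sphericity.

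**The concern.** Three angles taken from one person's airway are likely to resemble each other more than angles from different people. An analysis that fits the design removes the differences between people before comparing positions. Ordinary one-way ANOVA leaves them in the error term. Using each person as their own control is the main source of precision in a study of 20 people, so it matters that the plan does not commit to it.

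The label in section 4 does not help, since a reader could take it to mean separate groups. The open alternative in the test wording also leaves the choice of method unfixed. Under Step 7 the investigators analyse the results before the statistician does in Step 8, and nothing says the method is settled by then.

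Naming repeated-measures ANOVA would not fully close the gap. Its uncorrected form assumes that the three pairwise differences have equal variance, and full extension may not differ from the other two positions in the way that they differ from each other.

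**Working it through.** **Inputs from the documents.** n = 20 participants (section 8.1) and k = 3 positions (section 1.4; section 7, Step 6), so 20 × 3 = 60 angles per outcome. The significance level is 0.05 (section 8.3.1). The figure of 20 cannot be reproduced, because no effect size, SD, power or correlation is given.

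**Assumed inputs.** The total SD within each position is 1. The within-person correlation rho is equal for all pairs and ranges from 0 to 0.7. One position is shifted by d = 0.6 or 1.0 SD from the other two.

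**Error degrees of freedom.** Ordinary ANOVA: 60 − 3 = 57. With a participant term: (20 − 1)(3 − 1) = 38.

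**Standard error of a difference between two positions.** Ordinary ANOVA uses sqrt(2/20) = 0.316 SD whatever rho is. The correct value is sqrt(2(1 − rho)/20), which is 0.265, 0.224 and 0.173 at rho = 0.3, 0.5 and 0.7. The ratio is 1/sqrt(1 − rho) = 1.20, 1.41 and 1.83.

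**Type I error of ordinary ANOVA at nominal 5%, by simulation.** About 1.6 to 1.7% at rho 0.3, 0.4% at 0.5, and under 0.1% at 0.7.

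**Power.** With a participant term the noncentrality is n × (sum of squared deviations of the position means)/(1 − rho). For d = 0.6 the deviations are −0.2, −0.2 and 0.4, whose squares sum to 0.24, giving 20 × 0.24/(1 − rho) = 4.8/(1 − rho). For d = 1.0 it is 20 × (2/3)/(1 − rho) = 13.3/(1 − rho). Power for ordinary ANOVA comes from simulation.

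| Shift | rho | Ordinary ANOVA (2, 57 df) | Within-participant (2, 38 df) | Loss |
|---|---|---|---|---|
| 0.6 SD | 0 | 46–47% | 45–46% | none |
| 0.6 SD | 0.3 | 43% | 61% | 18 points |
| 0.6 SD | 0.5 | 40% | 76–77% | 36–37 points |
| 0.6 SD | 0.7 | 36% | 94% | 58 points |
| 1.0 SD | 0.3 | 92–93% | 97% | about 5 points |
| 1.0 SD | 0.5 | 95% | 99.6% | about 5 points |

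**Sphericity.** Let two positions correlate a with each other and b with the third, all variances 1. The two orthogonal contrasts then have variances v1 = 1 − a and v2 = (6 + 2a − 8b)/6, and epsilon = (v1 + v2)²/(2(v1² + v2²)).

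- a = 0.9, b = 0.3: v1 = 0.1, v2 = 0.9, epsilon = 1/1.64 = 0.61. Uncorrected repeated-measures ANOVA has type I error of about 7.5%. Greenhouse-Geisser correction brings it to about 4.8%.
- a = 0.7, b = 0.4: v1 = 0.3, v2 = 0.7, epsilon = 1/1.16 = 0.86. Type I error is about 5.7%.
- a = 0.7, b = 0.5: epsilon is about 0.91. Type I error is about 5.2 to 5.3%.

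With three positions epsilon cannot fall below 0.5, so the first case is strong. Milder patterns give about 5.5%.

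**The case against.** ANOVA is a family of methods that includes the repeated-measures form, and the wording also allows any other suitable test. Step 8 hands the data to a statistician ("Further anonymised data will be analysed by the statistician"), who would be expected to see that the scans are matched. This stands. A reader might infer that the 60 angles will be analysed as independent, but the text does not commit to that. The defect is an unspecified analysis, not a stated wrong one.

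A reader might also infer that a large loss of power is established. It is not. The loss runs from none to 58 points at 0.6 SD over the correlations shown, shrinks to about 5 points at 1.0 SD, and rests on inputs the documents do not supply. The inflation from non-sphericity likewise depends on an assumed covariance.

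Three further limits stand. Sections 8.3.1 and 8.3.2 mention only p values, so there is no planned confidence interval to call wrong. The error that ordinary ANOVA would bring is conservative when correlation is positive, and it could be put right from the same data. Finally, a reader might worry that the further anonymisation in Step 8 breaks the link between a person's scans. Section 9.2 already codes both participant and scan, which largely covers this, and nothing says the codes are removed.

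What the objection does not remove is that the primary analysis depends on a choice the plan has not made, and one permitted choice does not fit the design.

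**Conclusion.** The point holds as under-specification: the design is fully within-participant, and the analysis sections do not require a method that uses the matching. The standard-error ratio of 1/sqrt(1 − rho) follows from the design once rho is assumed equal across pairs. The power and type I error figures depend on assumed effect sizes and correlations and should be read as a range. Absence of any power loss needs rho near 0, which is unlikely for angles measured on the same larynx and trachea, though the documents offer no value either way. Should-fix: the remedy is simple, and the consequence arises only if an unsuitable form is chosen.

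**What to change.** In sections 8.3.1 and 8.3.2, replace the open test wording with one pre-specified within-participant analysis that applies to alpha, beta and delta. Either of these would serve:

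- repeated-measures ANOVA across the three positions with Greenhouse-Geisser correction; or
- a linear mixed model with position as fixed effect and participant as the repeated unit. An unstructured covariance would do the work of the sphericity correction; a participant intercept alone would not.

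Choose one and fix it before any angles are analysed. In section 4, describe the study as a single-group within-participant comparison of three positions.

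The cost is a few sentences in sections 4 and 8.3. No extra participants, scans or data are needed.
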